## **4.4 Treatment Assignment Procedures**

### **4.4.1 Randomization Procedures**

Prior to randomization, the inclusion and exclusion criteria will be reviewed, and any participant who does not meet the criteria will be discontinued from the trial. Randomization will be stratified across 3 clinical sites for a total of 200 randomized participants. Within each site, participants will be randomized in a 1:1 ratio of active drug to placebo within prespecified blocks. Randomization will be accomplished by a web-based randomization system developed and maintained by the data coordinating center. At the time of randomization, study staff, who will remain blinded to treatment assignment, will access the system, enter the participant's study identification number, and verify that the participant is eligible for randomization. The system will assign a randomization code that will indicate to the pharmacy the participant's treatment assignment.

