## 11.2 Sample Size Considerations

This study plans to randomize 200 participants, which will provide 94% power (alpha = 0.05) to detect a difference between a 27% reduction in pain index in the propranolol arm and a 9% reduction in the placebo arm (primary hypothesis). Assuming haplotype distributions and within-haplotype treatment effects that are similar to those observed in the pilot study, the same sample size would provide 61% power (alpha = 0.05) to detect an interaction between haplotype and treatment group (secondary hypothesis). The assumptions for these power calculations are shown in the following table. Power calculations were made using the GLMPOWER procedure in SAS, which assumes a data structure of one observation per person. This is a simplification of the situation that will occur with the linear mixed model described in Section 11.4.1 in which efficacy will be evaluated using a data structure in which most participants will have three observations per person. The simplified power calculations are shown here because conventional software for power calculations does not deal with the more complex situation of linear mixed models.

		Primary Hypothesis		Secondary Hypothesis					
COMT haplotype		All haplotypes		0 LPS copies		1 LPS copy		2 LPS copies	
Treatment arm		Drug	Placebo	Drug	Placebo	Drug	Placebo	Drug	Placebo
% of participants (N = 200)		50%	50%	15%	15%	25%	25%	10%	10%
Mean baseline pain index		3000	3000	3000	3000	3000	3000	3000	3000
Net change		-810	-270	-1350	-270	-810	-270	-270	-270
Percentage change		-27	-9	-45	-9	-27	-9	-9	-9

\* LPS stands for low pain sensitive, one of the major haplotypes of *COMT*. The standard deviation for the mean baseline pain index is estimated to be 1190. The net change takes into account a 10% lost-to-follow-up rate and imputation using the last observation carried forward approach.

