#### **11.4.2 Analysis of the Secondary Hypotheses**

To test the secondary hypothesis of gene-by-treatment interaction, the linear mixed model described for the primary analysis will be extended by adding three sets of predictor variables: (1) the number of COMT LPS haplotypes (0, 1, or 2) will be modeled as a fixed effect, either as a continuous variable, or as a 3-level categorical variable (i.e., two dummy variables), with the decision based on the approach that optimizes model fit, as determined by Akaike's Information Criterion; (2) two-way interactions between haplotype effect and treatment allocation and between haplotype effect and visit sequence; and (3) a three-way interaction term between the

---

haplotype effect, treatment allocation, and visit sequence. The gene-by-treatment interaction at V4 is the interaction of interest.

For descriptive purposes, an analogous model will generate efficacy estimates according to COMT ValMet genotype as the genetic marker instead of the number of LPS haplotype. In an analogous manner, the genotype will be coded either as a continuous or categorical variable based on optimal model fit. Efficacy estimates will be calculated for descriptive purposes only; there will be no hypothesis tests for the interaction terms.

Another descriptive set of secondary analyses will adapt the approach for analysis of the LPS haplotype, restricting the model to non-Hispanic whites. This is consistent with the approach of some genetic researchers who advocate racial-group restriction as a preferable analytic method to control for population stratification.

Linear mixed models will be used to evaluate effects of treatment group allocation on secondary efficacy variables (see Statistical Analysis Plan for full details).

Linear regression or other appropriate statistical modeling will evaluate the effects of treatment on the number of days in which rescue medications for TMD-related pain reportedly were used and on the number of days in which over-the-counter analgesics (namely, NSAIDs, acetaminophen, and aspirin) reportedly were used for treatment of any type of pain.

See the Statistical Analysis Plan for more details on these secondary analyses.

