2.6 Sample Size Determination

This study plans to randomize 200 participants, which will provide 94% power (alpha = 0.05) to detect a difference between a 27% reduction in pain intensity in the propranolol arm and a 9% reduction in the placebo arm (primary hypothesis). Assuming haplotype distributions and within-haplotype treatment effects that are similar to those observed in the pilot study, the same sample size would provide 61% power (alpha = 0.05) to detect an interaction between haplotype and treatment group (secondary hypothesis).

Power calculations were made using the GLMPOWER procedure in SAS, which assumes a data structure of one observation per person. This is a simplification of the situation that will occur with the linear mixed model, described in Section 10.4.1, where efficacy will be evaluated using a data structure where most participants will have three observations per person. The simplified power calculations are shown here because conventional software for power calculations does not deal with the more complex situation of linear mixed models.

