To test the secondary hypothesis of gene-by-treatment interaction, the linear mixed model described for the primary analysis will be extended by adding three sets of predictor variables: (1) the number of COMT LPS haplotypes (0, 1, or 2) will be modeled as a fixed effect (both as a continuous variable and as a categorical variable); (2) two-way interactions between haplotype effect and treatment allocation and between haplotype effect and visit sequence; and (3) a threeway interaction term between the haplotype effect, treatment allocation, and visit sequence. The gene-by-treatment interaction at V4 is the interaction of interest. A contrast statement within the mixed model will test for a gene-by-treatment interaction at V4 with a P-value ≤ 0.05 considered statistically significant. Both an unstructured and compound symmetry variance structure, as well as, fitting the haplotype variable as a continuous (linear) and a categorical variable will be tested. The statistical model with the lowest Akaike information criterion will consider the best model and used for inference testing. Residual analysis will be used to confirm that there are no major violations of model assumptions. Model adjusted means will be reported with their 95% confidence intervals. For descriptive purposes, a second set of secondary analyses will be performed on the valine allele of the *COMT* gene using valine allele (Val/Met allele) counts in an identical manner as for the LPS haplotype counts described. A third set of secondary analyses will adapt the approach for analysis of the LPS haplotype, restricting the model to non-Hispanic whites. This is consistent with the approach of some genetic researchers who advocate racialgroup restriction as a preferable analytic method to control for population stratification.

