8.3.3 Exploratory Efficacy Analyses

The mixed model described for the secondary hypothesis of the LPS and Val/Met haplotypes will be modified by specifying genetic variants for the *COMT* promoter, *ADRB2* gene, and *ADRB3* gene. Other genetic variants may also be included in the mixed model. The only difference in these mixed model analyses is that the *ADRB2* and *ADRB3* gene types will be included as categorical fixed effects rather than the linear continuous fixed effects in the LPS and Val/Met haplotype mixed models.

Other stratum-specific estimates of treatment effect will be explored in an analogous manner, namely through the use of mixed models in which the stratification variable is a categorical fixed effect. Each stratum will be a mutually exclusive category of study participants, classified according to the following characteristics assessed either at V0 or V1:

- Body Mass Index, computed from measurements recorded at V1, will be used to create two strata, with the dichotomy based on one of two established thresholds ≥25 or ≥30. The decision as to which threshold will be made after inspecting the distribution of BMI, and select the threshold that is closest to the median.
- Smoking status, assessed using the Smoking questionnaire completed at V0, will be used to create two strata: current tobacco smokers or not (the latter therefore including former smokers and never smokers). Smokeless tobacco and other sources of nicotine will not be used for this classification.
- Migraine headache will be classified using responses to the headache questionnaire (HAQ) administered at V1. Two strata will be created, classified according to presence or absence of one or more of four types of migraine sub-types (Migraine without aura, Migraine with aura, Chronic migraine, or Probable migraine without aura).
- Degree of examiner-assessed tenderness to body palpation, recorded at Item 4 of the Fibromyalgia Questionnaire at V0, will be used to create two strata, based as closely as possible on a median split of the total number of tender points.

Version 3.0 Page 17 of 25

- Published scoring algorithms will be used to compute the catastrophizing subscale of the revised Coping Strategies Questionnaire (CSQ-R) measured at V1. The two strata will be based as closely as possible on a median split of the subscale score.

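### The 61% interaction power is that of a 1-df linear-copies test; the AIC-chosen test in the plan does not have 61% power at a true 5% level

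*Protocol*

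**What the plan says.** Protocol 11.2 states that "the same sample size would provide 61% power (alpha = 0.05) to detect an interaction between haplotype and treatment group". A table beside it sets out 0, 1 and 2 LPS copies as three groups. SAP 2.6 repeats the figure without the table: "sample size would provide 61% power (alpha = 0.05) to detect an interaction between haplotype and treatment group". Neither section says how haplotype was coded or how many degrees of freedom the test has.

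The analysis sections leave the coding open. Protocol 11.4.2 enters the number of LPS copies "either as a continuous variable, or as a 3-level categorical variable (i.e., two dummy variables"), and Akaike's criterion decides. SAP 8.3.2 does the same, across two covariance structures as well: "fitting the haplotype variable as a continuous (linear) and a categorical variable will be tested". The model with the lowest AIC supplies the Visit 4 interaction contrast, judged at P ≤ 0.05. No multiplicity correction is made. Neither document says whether the AIC comes from ML or REML fits.

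SAP 8.3.3, on the exploratory genes, writes as if the coding were already settled. It says those genes will be categorical "rather than the linear continuous fixed effects in the LPS and Val/Met haplotype mixed models".

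**The concern.** A power figure belongs to a particular test. Here one figure is printed while two tests with different degrees of freedom are allowed, and the trial data choose between them. Choosing a model on the data and then testing in it at the nominal level can raise the type I error. AIC values from REML fits with different fixed effects are not comparable at all.

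This is the first-listed secondary objective and the question in the trial's title. One P-value, without multiplicity adjustment, settles it. A non-significant interaction would be read against 61% power that the test may not have had. A significant one would be read as a 5% finding when the selection step may have made it somewhat looser.

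**Working it through.** **Inputs (Protocol 11.2 unless stated)**
- N = 200, randomized 1:1 (Protocol 4.4.1).
- Drug/placebo cell sizes for 0, 1 and 2 copies, from the printed percentages: 30/30, 50/50, 20/20.
- Net change, drug/placebo: -1350/-270, -810/-270, -270/-270. Differences d: -1080, -540, 0, a step of 540 per copy.
- SD 1190. It is printed for the baseline index; no SD of change is given, so it serves as the residual SD.
- One observation per person. The 10% loss is said to be already in the net changes, so N stays at 200.

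**Noncentrality**

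Weighted mean difference = 0.3(-1080) + 0.5(-540) + 0.2(0) = -594.

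NCP = Σ m(d + 594)² / (2 × 1190²), with m = 30, 50, 20 per arm
= (30 × 486² + 50 × 54² + 20 × 594²) / 2,832,200
= 14,288,400 / 2,832,200 = 5.045.

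Because d is exactly linear in copies, the linear coding gives the same value: 540² × Σ m(k - 0.9)² = 291,600 × 49 = 14,288,400. The second degree of freedom carries no signal under these effects.

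**Power at two-sided 0.05 (noncentral F)**

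| Test | df | Power |
|---|---|---|
| Linear copies × treatment | 1, 196 | 60.8% |
| Three groups × treatment | 2, 194 | 50.1% |

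The first row reproduces the printed 61%; the second is 11 points lower. With N = 180 the values are 56.3% and 45.7%.

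**The AIC rule, ML fits**

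With one observation per person, the 3-level model has two more mean parameters (6 against 4), so it wins only if it lowers the deviance by more than 4. If the truth is linear, the large-sample chance of that is P(χ²₂ > 4) = e⁻² = 0.135. Results over 100,000 simulated trials for each scenario:

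| | Tabled effects | No interaction (-540 in every group) |
|---|---|---|
| 3-level coding chosen | 14.4% | 14.6% |
| Rule rejects at 0.05 | 61.8% | 7.3% |

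Holding type I error at 5% requires a cut-off of about 0.034, and power is then 55.5%.

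**The AIC rule, REML fits**

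The REML criterion depends on the number of fixed effects and on the units of the outcome. Going from 4 to 6 fixed effects removes about 2 ln(2π × 1190²) + 2 = 34.0 from -2 log-likelihood. The design term gives back only 2 ln(30 × 50 × 20) - 2 ln(100 × 49) = 20.6 - 17.0 = 3.6. The 3-level model therefore starts about 30 units ahead for reasons unrelated to fit. It was chosen in every simulated trial: power 50.1%, type I error 5.0%.

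**Three visits**

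A simulation with three visits (3,000 runs per setting, between-visit correlation 0.5 to 0.7, complete data) gave power of 0.60 to 0.63 under ML and 0.49 to 0.52 under REML. There the 3-level coding adds six parameters: one each for haplotype and haplotype × treatment, and two each for haplotype × visit and the three-way term. The large-sample chance of selecting it is P(χ²₆ > 12) = e⁻⁶(1 + 6 + 18) = 0.062, in line with the roughly 7% observed. Selection is rarer than in the one-observation case, so the type I error inflation should be smaller than the 7.3% above. Its size was not estimated.

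**The case against.** The figure itself is sound. 61% reproduces at the stated alpha for a coding that the plan names first, that matches the hypothesis in Protocol 11.1.2 (efficacy varying with the number of LPS haplotypes) and that SAP 8.3.3 takes for granted. This stands: what is missing is a specification, and the arithmetic is not in error.

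A reader might infer that the trial really has 50% power, or that the stated power contradicts the decision rule. The documents do not support either. The rule is a choice by AIC and does not prescribe the 3-level test. With ML-based AIC it rejects about as often as printed under the tabled effects; the cost there is type I error. The 50% applies only to an always-3-level plan or to REML-based AIC. SAP 8.3.1 names Proc Mixed with the Kenward-Roger adjustment, which makes REML plausible, but nothing says which was intended.

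The 3-level test also has a purpose. Protocol 2.1.5 reports protection from a single LPS haplotype and expects most benefit in non-carriers. For an assumed carrier pattern of -1080, 0, 0 with the same cells and SD, the 3-level test has about 75% power against 68-69% for the linear one. Making the linear test the only one is therefore a trade-off.

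Finally, the inputs are rough. Moving the SD by 10% either way shifts the 1-df power to 70% or 53%, nearly as much as the gap between codings. Protocol 11.2 itself calls the calculation a simplification. This limits how much weight any single figure can bear, but not the need to say which test it describes.

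**Conclusion.** The point holds in a limited form. Of the two codings that the plan allows, only the 1-df linear-copies test gives the printed 61% at alpha 0.05 on the printed inputs; the 3-level test gives 50%, and neither document says which is meant. In the one-observation setting that the plan's power calculation uses, the rule of choosing by AIC and then testing does not deliver 61% at a true 5% level under either estimation method: about 62% with type I error near 7% (55.5% once calibrated) under ML, and 50% under REML.

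This rests on the tabled effects being right, on the baseline SD standing in for the residual SD, and on one observation per person. In the three-visit model the ML inflation should be smaller, which would bring the rule closer to its printed power. Neither the sample size nor the primary analysis is affected.

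**What to change.** - **Protocol 11.2 and SAP 2.6:** say that 61% is for a two-sided 0.05, 1-df test of treatment by number of LPS copies at Visit 4, and that the 2-df test on three groups has 50%. Carry the assumptions table into the SAP.
- **Protocol 11.4.2 and SAP 8.3.2:** fix one coding for the deciding P-value before unblinding. The linear 1-df contrast fits the tabled effects, the stated hypothesis and SAP 8.3.3. The 0/1/2-copy adjusted means can then be reported descriptively.
- **If the AIC choice is kept:** require ML fits for comparing codings, control the type I error of the selection step, and restate the power for that whole procedure, preferably by simulating the three-visit model.
- **SAP 8.3.2 and 8.3.3:** reconcile the description of the LPS coding.

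Fixing the coding costs wording only, with no added participants or data. Its price is lower power if the gene effect is not additive. Keeping the AIC choice costs a short simulation and, once the level is controlled, probably a less favourable power figure.

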## 11.3 Analysis Samples

### 11.3.1 Intention-To-Treat Sample

Consistent with the primary statistical method that will use a linear mixed model (also called "mixed model repeated measures" model), the intention-to-treat sample is defined as all study participants who have at least one valid measurement of the primary endpoint at Visit 2 or later. A "valid" assessment for the primary endpoint is defined as at least 4 daily reports of pain intensity and duration collected in the 7-day period prior to the visit (Section 2.5.1). Treatment group allocation will be defined as the study arm into which the subject was randomized regardless of the actual study treatment received. By necessity, the intention-to-treat sample excludes participants who provide no data for the primary endpoint after randomization. Note that follow-up assessments will be included in the intention-to-treat analysis when sufficient diary data are collected at the follow-up assessment, even if there were protocol violations. Likewise, the intention-to-treat sample will include all available follow-up assessments from any discontinued participants.

### 11.3.2 Per-Protocol Sample

Secondary statistical analysis of the primary hypothesis will be in the spirit of per-protocol analysis. The per-protocol sample will be a subset of the intention-to-treat sample, excluding any assessments made at or after a visit at which the participant is found to have any protocol deviation listed in Section 5.8. In addition, all assessments for participants whose compliance with study medication is less than 60% over all study visits will be excluded from per-protocol analyses.

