## **2.5 Study Outcome Measures**

### **2.5.1 Primary Outcome Measures**

The primary endpoint will be a weekly mean pain index, representing the arithmetic mean of daily pain index values during the week prior to the study visit. The pain index will be computed during analysis as the product of the pain intensity score, reported on a 0-100 numeric rating scale (NRS), multiplied by the pain duration score, reported on a 0-100 percentage scale, each as reported in the Daily Symptom Diary. The weekly mean pain index will be computed for the week prior to randomization and for each week during the treatment phase. The weekly mean pain index will be calculated if a participant completes at least 4 of the 7 daily reports of pain intensity and duration during the 7-day period prior to the visit. When there are fewer than 4 daily reports, the weekly mean pain index will be considered missing.

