## **5.7 Concomitant Medications and Therapies**

Prior and concomitant medication information will be collected for all participants for the 30 days prior to the Screening and Baseline Visit and during the study. Information collected will include medication, total daily dose, start date, stop date (if applicable), and primary reason for use. Information about treatment with injection therapy, acupuncture, biofeedback, TENS, and occlusal splint therapy will also be collected for all participants for the 30 days prior to the Screening and Baseline Visit and during the study.

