### 11.4.1 Analysis of the Primary Hypothesis

The primary statistical analysis to evaluate the primary hypothesis will use all data from the intention-to-treat analytical sample in a linear mixed model. During the analysis of the primary hypothesis, treatment allocation will be masked (i.e., groups will be labeled A and B). Treatment allocation will be unmasked for further analyses.

---

The dependent variable will be the participant's change in the weekly pain index, computed as the weekly pain index at the follow-up visit (i.e., at Visit 2, Visit 3, or Visit 4) minus the Visit 1 weekly pain index. Explanatory variables will comprise fixed factors and a continuous covariate. The fixed factors will include the following: (a) treatment allocation (two categories) (b) visit sequence (three categories); (c) interaction of treatment allocation and visit sequence (two dummy variables); and (d) covariates of study site (three categories), sex (two categories) and race/ethnicity (probably three categories: non-Hispanic White, non-Hispanic Black, and other/multiple racial or ethnic groups – the final number of conditions will be dictated by the frequency distribution of race/ethnicity in the study sample). The baseline score collected at Visit 1 will be the continuous covariate, modeled as a fixed effect. The study participant will be modeled as a random factor.

In a linear mixed model containing all predictor variables including the interaction terms for visit and treatment allocation, the primary treatment effect will be tested at Visit 4. The null hypothesis of no treatment effect will be rejected if the P-value at Visit 4 is  $\leq 0.05$ . For descriptive purposes (and regardless of the P-value for efficacy at Visit 4), efficacy estimates at each visit (2, 3 and 4) will be described in terms of adjusted means and 95% confidence intervals.

If the propranolol treatment arm has a greater reduction in the weekly pain index than the placebo arm at Visit 4, a threshold of "responder analysis" will be undertaken to estimate the odds of at least a 30% reduction, relative to Visit 1, in the pain index at Visit 4. Likewise, another threshold of responder analysis will describe the odds of experiencing at least a 50% reduction. These estimates will be calculated from a logistic model in which the dependent variable is a binary variable that dichotomizes the change score at the appropriate threshold (i.e.,  $\geq 30\%$  or  $\geq 50\%$ ).

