4.2 Per-Protocol Population

As stated in Section 11.3.2 of the protocol, the per-protocol (PP) sample will be a subset of the ITT sample, excluding any assessments made at or after a visit at which the participant is found to have any major protocol deviation as listed in Section 5.2 below and excluding all assessments for participants whose compliance with study medication is less than 60% over all the study visits.

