5.2 Protocol Deviations

The protocol deviations listed below are related to the use of investigational product and concomitant therapies and will be considered major protocol deviations. These deviations will exclude a participant's data from the PP analysis (Section 4.2).

Version 3.0 Page 9 of 25

- Participant is unable to reach the maintenance dosage of the study drug or placebo or is unable to remain on the maintenance dosage.
- Initiation of opioid medications.
- Initiation of TMJ surgical treatment (including TMJ arthrocentesis).
- Initiation of therapeutic injections for the management of pain.
- Initiation of occlusal appliance therapy.
- Initiation of any of the following non-pharmacological therapies: acupuncture, biofeedback, and/or TENS.
- Initiation after Visit 1 and usage between Visits 1 and 4 of short-acting, non-prescription analgesics (e.g., NSAIDs, aspirin, and/or acetaminophen) for pain that exceeds the definition of episodic use as described in Section 5.7.1 of the protocol.

These and other types of protocol deviations will be reported during the study. The types of protocol deviations will be summarized descriptively for both the Safety and ITT populations by treatment group. A listing of the protocol deviations of individual participants will be included in the participant listings.

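### The per-protocol rule starts exclusion at the visit where a deviation is found, not when it began, so a deviation found late leaves affected endpoint weeks in the per-protocol analysis

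*Protocol*

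**What the plan says.** Protocol 11.3.2 starts from the intention-to-treat participants and forms the per-protocol sample by "excluding any assessments made at or after a visit at which the participant is found to have any protocol deviation listed in Section 5.8". SAP 4.2 has the same rule, "excluding any assessments made at or after a visit at which the participant is found to have any major protocol deviation", and takes its list of deviations from SAP 5.2. SAP 5.2 says that these deviations exclude a participant's "data from the PP analysis (Section 4.2"), which sends the reader back to the same rule. SAP 11 declares no change from the protocol. Neither document mentions the date on which a deviation began. Participants below 60% compliance with study medication lose all their assessments under a separate provision, which is not at issue here.

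Three other parts of the plan bear on how the rule works:

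- **Endpoint.** Protocol 2.5.1 defines the weekly index as "representing the arithmetic mean of daily pain index values during the week prior to the study visit". In Protocol 11.4.1 the dependent variable is "computed as the weekly pain index at the follow-up visit (i.e., at Visit 2, Visit 3, or Visit 4"), minus the Visit 1 value. Visit 5 does not enter the model.
- **Detection.** Concomitant medications and specified therapies are recorded at Visits 2, 3, 4 and 5 (Protocol 6.3.2 to 6.4).
- **Dates.** For medications, Protocol 5.7 states: "Information collected will include medication, total daily dose, start date, stop date (if applicable), and primary reason for use". For injections, acupuncture, biofeedback, TENS and splints it says only that information about the treatment is collected.

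**The concern.** The analysed value covers the 7 days before a visit. Whether it is free of disallowed co-treatment depends on whether the deviation had begun by then, not on when staff learned of it. A rule keyed to discovery gives the right answer only if discovery is prompt.

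The per-protocol analysis is the only planned repeat of the primary hypothesis in another sample (Protocol 11.4.1, SAP 8.3.1). Its purpose is to show the treatment effect without the listed deviations. Weeks known to be affected but kept in would pull the per-protocol result toward the intention-to-treat result. SAP 8.3.1 then uses agreement between the two as the condition for running all later analyses on the intention-to-treat population only, so agreement would be less informative than it looks.

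**Working it through.** No sample size, power or alpha in the plan depends on this rule, so there is no stated figure to reproduce. The check is to apply the rule to cases.

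**1. Inputs.** Nominal visit days are 7, 35, 63 and 77 for Visits 2 to 5 (Appendix A). The endpoint weeks are the 7 days before Visits 2, 3 and 4: Days 0–6, 28–34 and 56–62. The model set is {V2, V3, V4}. Following the plan's own labelling, each weekly mean belongs to the visit it precedes. A deviation, once begun, is taken to continue.

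**2. Rule.** A week is affected if its last day is on or after the onset day. Under the current text it is removed only if its visit is the visit of discovery or a later one. The retained affected weeks are therefore the affected weeks of visits before discovery.

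**3. Result.** Each cell lists the affected endpoint weeks that stay in the per-protocol set.

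| Onset day | Affected weeks | Found at V2 | Found at V3 | Found at V4 | Found at V5 |
|---|---|---|---|---|---|
| 3 | V2, V3, V4 | none | V2 | V2, V3 | V2, V3, V4 |
| 10, 20 or 30 | V3, V4 | – | none | V3 | V3, V4 |
| 40, 50, 58 or 62 | V4 | – | – | none | V4 |

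The first filled cell in each row is discovery at the next scheduled visit, and there nothing affected is kept. Every later cell keeps something. For discovery at Visit 5, the excluded set {V5} and the model set {V2, V3, V4} do not overlap, so nothing is removed. A deviation that comes to light at monitoring or data review has no visit of discovery at all; read literally, the rule again removes nothing from the model.

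A retained Visit 3 week also bears on the Visit 4 contrast. There is no imputation (SAP 8.1), so once a participant's Visit 4 value is deleted, the retained Visit 3 value helps to inform the Visit 4 estimate through the mixed model.

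**4. Size.** The shift in the Visit 4 contrast from retained Visit 4 weeks is roughly p × d. Here p is the between-arm excess in the proportion of participants with such a week, and d is the change in the index caused by the co-treatment. The documents give neither. For scale only, assume d = 540, borrowed from the design difference in Protocol 11.2 (810 − 270), and an excess p in the placebo arm of 2%, 5% or 10%:

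- 0.02 × 540 = 10.8 points
- 0.05 × 540 = 27 points
- 0.10 × 540 = 54 points

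With the SD of 1190 given in Protocol 11.2 and 100 per arm, the standard error of a difference is about 1190 × √(2/100) = 168. The shifts are then about 0.06, 0.16 and 0.32 standard errors. These are assumptions, not estimates. The shift is toward zero only if co-treatment lowers pain and is commoner on placebo; an excess on propranolol would reverse it.

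**5. Under an onset-based rule.** No affected week is kept in any cell. Where discovery is prompt, the per-protocol set is the same as now for every onset day tested.

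**The case against.** The strongest reply is that the gap needs a detection failure. Medications and therapies are asked about at every treatment visit. Analgesic use is quantified at each visit (Protocol 5.7.1.1), and its limit runs only from Visit 1 to Visit 4. Study drug containers are returned and compliance is assessed at Visit 4. For the Visit 4 week to be wrongly kept, a deviation must be missed at Visit 4 and surface afterwards. This stands, and it is why the effect is probably small. It does not remove the gap: the plan schedules a further review at Visit 5, allows diaries to be returned by mail (Protocol 7.1.10) and provides for monitoring of records (Protocol 10), yet does not say what follows if any of these finds an earlier deviation.

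A reader might infer that affected diary weeks stay in generally, the Visit 4 week included, because diary entries are written before the visit at which a deviation is found. The documents do not support that. Protocol 11.4.1 calls the preceding week's mean the index at the visit, and Protocol 11.3.1 includes follow-up assessments "when sufficient diary data are collected at the follow-up assessment, even if there were protocol violations". On that labelling, discovery at Visit 4 removes the Visit 4 week. The plan does not define when a diary-based assessment is made, so a line saying so is worthwhile, but the entry-date reading is the weaker one.

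A reader might also infer that the trial's conclusion is at risk through the SAP 8.3.1 comparison. It is not. The primary test uses the intention-to-treat sample, which SAP 8.3 already makes the default for all analyses. False agreement would leave later analyses on that default.

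**Conclusion.** The point holds for late discovery only. Protocol 11.3.2 and SAP 4.2 start exclusion at discovery, and SAP 5.2 does not repair this. A deviation that began before Visit 4 but is first found at Visit 5 or at data review leaves the Visit 4 week in; one that began before Visit 3 but is found at Visit 4 leaves the Visit 3 week in. Discovery at the next scheduled visit removes the affected week, Visit 4 included, provided the diary mean is taken to belong to the visit it precedes.

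The effect on the per-protocol estimate cannot be sized, because no late-detection rate and no co-treatment effect are given; it is probably small. Only a secondary analysis is touched. Even so, this is more than a missing detail: the stated rule keeps weeks that the trial's own records may show to be affected, and it is cheap to correct before the per-protocol set is programmed.

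**What to change.** In SAP 4.2, and in Protocol 11.3.2 to match, state two things. First, the 7-day diary mean belongs to the visit it precedes. Second, the per-protocol sample excludes any visit's weekly mean whose 7-day window ends on or after the start of a Section 5.8 deviation, and all later ones, whenever the deviation is found.

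Define the start as follows:

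- **Recorded date available (for example, medications):** use it.
- **Only the interval between visits known, as may be so for non-drug therapies:** apply the exclusion from the first visit after the earliest possible start.
- **Dosage deviation:** use the date on which the participant is recorded as unable to reach or remain on the maintenance dosage. A single missed capsule should not trigger exclusion; Section 5.8 does not describe that, and compliance has its own 60% criterion.
- **Analgesic use:** use the visit interval in which the Section 5.7.1 limit is exceeded if daily dates are not available. The plan does not show that they are.

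The cost is a short wording change in each document, some date-based programming and slightly fewer per-protocol assessments. The intention-to-treat analysis does not change.
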